### **Subsequent Post-remission Therapy (Cycle 2+)**

Patients without clinical or laboratory evidence of relapse will continue to receive therapy with DEC-C/venetoclax for maintenance of response (See [Figure 1](#) and [2](#)). Subsequent post-remission cycles will be initiated after evidence of count recovery, defined as:

Platelets  $\geq 50,000/\text{mm}^3$  /  $50.0 \times 10^9/\text{L}$   
Neutrophils  $\geq 1000/\text{mm}^3$  /  $1 \times 10^9/\text{L}$

In patients who recover counts within 6 weeks of CxD1, and are otherwise tolerating therapy, subsequent post-remission cycles will occur at the same dose level.

If count recovery is delayed >6 weeks beyond CxD1, patients will be reduced by one dose level (e.g., a patient with count recovery lasting 7 weeks after post-remission C1 will dose C2 at dose level -1).

For patients with delayed count recovery (>6 weeks) at dose level -3, discussion with the study chair is recommended.

**Table 6: Venetoclax/DEC-C Dose Level Summary (Post-remission Phase)**

DOSE LEVEL	VENETOCLAX	DEC-C
1	400mg/day dosed continuously	100mg/35mg Days 1-5
-1	400mg/day 21/28 days	100mg/35mg Days 1-4
-2	400mg/day 14/28 days	100mg/35mg Days 1-3
-3	400mg/day 7/28 days	100mg/35mg Days 1, 3, and 5

\* Cycles are every 28 days.

Patients who are experiencing low-grade tolerability symptoms and are deriving clinical benefit from the treatment may have their dose reduced, or subsequent cycle delayed, at the discretion of the PI. Dose reductions should be done in accordance with [Table 6](#). Patients whose dose or schedule is reduced may subsequently be re-escalated to the previous dose upon improvement of the tolerability, at the discretion of the PI. PI may consult with the study chair as necessary.

### 5.2.7 Dose modifications

**Table 7: Toxicity Dose Adjustment Guidelines**

Event	Occurrence	Action
Grade 4 neutropenia with or without fever or infection  OR  Grade 4 thrombocytopenia	Occurrence prior to achieving remission*	
 
Transfuse blood products, administer prophylactic and treatment anti-infectives as clinically indicated.
 
In most instances venetoclax and DEC-C cycles should not be interrupted due to cytopenias prior to achieving remission
 

	First occurrence after achieving remission and lasting ≤ 7 days	
 
Delay subsequent treatment cycle of
 

		
venetoclax and DEC-C and monitor blood counts.
 
 
• Administer G-CSF if clinically indicated (see Section 5.2.6.2)
 
• Once toxicity has resolved to <math>\leq</math> Grade 2, resume venetoclax/ DEC-C at the same dose.
 

	
Subsequent occurrences in cycles after achieving remission and lasting <math>\geq</math> 7 days.
	
 
• Delay subsequent treatment cycle of venetoclax and DEC-C and monitor blood counts.
 
• Administer G-CSF if clinically indicated (see Section 5.2.6.2)
 
• Once toxicity has resolved to <math>\leq</math> Grade 2, resume venetoclax and DEC-C at one dose level lower (see Table 6)
 

\*Consider interim bone marrow biopsy for patients who may have achieved early remission

Table obtained from current venetoclax USPI. Modifications relevant to this study are indicated in underline and bold.

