#### Initiating Post-remission Phase (Cycle 1)

Patients will begin the post-remission phase of the study after achieving blast clearance from their marrow. Patients with marrow aplasia must recover peripheral blood counts with ANC of  $\geq 1000/\text{mm}^3$  /  $1 \times 10^9/\text{L}$ . Patients with cellular marrows may proceed to the post-remission phase of the study without count recovery if the treating physician believes the cellularity is disease related. Discussion with the study chair is recommended.

Patients with marrow aplasia on C1D22 or C2D22 BMBx will have venetoclax interrupted until the absolute neutrophil count (ANC) recovers to  $\geq 1000/\text{mm}^3$  /  $1 \times 10^9/\text{L}$ . If persistent grade 4 cytopenias, repeat BMBx will be performed at D42. If persistent marrow aplasia without disease, patients will be managed expectantly until  $\geq 1000/\text{mm}^3$  /  $1 \times 10^9/\text{L}$ . A BMBx will be repeated every 6 weeks until ANC recovery. At that time, patients will enter the post-remission phase (See [Figure 2](#)).

To proceed with each cycle of post-remission therapy, platelets/ANC must be improved to grade 2 or higher:

Platelets  $\geq 50,000/\text{mm}^3$  /  $50.0 \times 10^9/\text{L}$   
Neutrophils  $\geq 1000/\text{mm}^3$  /  $1 \times 10^9/\text{L}$

Venetoclax and DEC-C are generally intended to be dosed in combination but may be separably dosed for up to 28 consecutive days. The dose levels of venetoclax and DEC-C are indicated in [Table 5](#).

In the event of an adverse event deemed by the study physician as unrelated to protocol-indicated treatment, the study physician may choose to precautionarily interrupt venetoclax and/or DEC-C for up to 28 days, but no dose reduction of either agent should occur.

Venetoclax and/or DEC-C may be delayed for any adverse event, laboratory abnormality, or intercurrent illness which, in the judgment of the investigator, warrants delaying the dose of DEC-C and/or venetoclax. If either or both drugs are interrupted for  $>4$  weeks for reason other than treatment-related cytopenias, discussion with the study chair is recommended.

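### After remission, Table 7 and the 6-week count-recovery rule can give one patient opposite dose instructions, and nothing says which prevails

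*Combined protocol and SAP*

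**What the plan says.** Section 5.2.6.3, under Subsequent Post-remission Therapy (Cycle 2+), decides the next dose by time to count recovery. For patients "who recover counts within 6 weeks of CxD1, and are otherwise tolerating therapy, subsequent post-remission cycles will occur at the same dose level". On the other side of the cut, "If count recovery is delayed >6 weeks beyond CxD1, patients will be reduced by one dose level". Neither sentence refers to the grade of the cytopenia, how long it lasted, or whether it was a first or repeat event.

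Section 5.2.7, Table 7, decides the next dose by occurrence number and duration of grade 4 neutropenia or thrombocytopenia. Its two post-remission rows are:

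- "First occurrence after achieving remission and lasting" 7 days or less: delay the next cycle, then resume at the same dose once the toxicity is grade 2 or lower.
- "Subsequent occurrences in cycles after achieving remission and lasting" 7 days or more: delay the next cycle, then, at the same recovery grade, "resume venetoclax and DEC-C at one dose level lower", with a reference to Table 6.

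The additional considerations on hematologic toxicity that follow Table 7 send post-remission dose reductions to Table 6. They do not say which of the two triggers governs.

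**The concern.** Both rules apply in the post-remission phase, both choose the dose of the next cycle, and both use the Table 6 levels. They rest on different features of the same event, so a patient can satisfy one rule's condition for keeping the dose and the other's for lowering it.

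The study is multi-center (Sections 6.1 and 10.6). Two sites could treat identical patients differently, each believing that it follows the protocol, and Section 10.6.10 could not be applied consistently to call either a deviation. What is at stake is consistency of post-remission dosing, the reading of safety and exposure summaries (safety and tolerability is a secondary objective), and the Section 8.2.2 correlatives that use dosing as a variable.

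**Working it through.** The plan states no figure to reproduce. The check sets the rules side by side and asks whether one patient can meet both.

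**Are the recovery thresholds the same?** Section 5.2.6.3 says: "To proceed with each cycle of post-remission therapy, platelets/ANC must be improved to grade 2 or higher", and lists platelets of at least 50,000/mm³ and neutrophils of at least 1000/mm³. The Cycle 2+ text repeats those two values. Table 7 waits for grade 2 or lower. As the protocol grades it, the endpoint is the same, so a different definition of recovery does not explain the clash.

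**Day count.** 6 weeks × 7 = 42 days from day 1 of the cycle. Since "Cycles are every 28 days", that is 42 − 28 = 14 days past the nominal cycle. The Cycle 2+ text sets no earliest recovery day, so any recovery up to day 42 counts as within 6 weeks.

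**All combinations** (first recovery column: patient tolerating treatment in other respects):

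| Post-remission grade 4 episode | Recovered by day 42 | Recovered after day 42 |
|---|---|---|
| First, ≤ 7 days | Table 7 same; Cycle 2+ same: agree | Table 7 same; Cycle 2+ one lower: **conflict** |
| First, > 7 days | Table 7 silent; Cycle 2+ same | Table 7 silent; Cycle 2+ one lower |
| Later, < 7 days | Table 7 silent; Cycle 2+ same | Table 7 silent; Cycle 2+ one lower |
| Later, ≥ 7 days | Table 7 one lower; Cycle 2+ same: **conflict** | Table 7 one lower; Cycle 2+ one lower: agree |

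Of the eight cells, both rules speak in four. They agree in two and conflict in two. In the other four, only the Cycle 2+ rule speaks.

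**Example of the first conflict (days assumed).** A second post-remission grade 4 neutropenia runs from day 15 to day 24, which is 24 − 15 + 1 = 10 days. Counts recover by day 35, and there is no other toxicity. Since 10 ≥ 7, Table 7 lowers the dose by one level. Since 35 ≤ 42, the Cycle 2+ text keeps it.

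**Example of the reverse conflict.** The Cycle 2+ text gives its own illustration: recovery taking 7 weeks after post-remission cycle 1 leads to level -1 in cycle 2. Assume that this was the patient's first post-remission episode and that only 7 days or less of it was grade 4, with slow improvement through grade 3. Recovery comes at 7 × 7 = 49 days, beyond 42, so the Cycle 2+ text lowers the dose. Table 7 resumes at the same dose.

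**What one level means in Table 6, per 28-day cycle:**

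| Step | Venetoclax days | DEC-C days |
|---|---|---|
| 1 to -1 | 28 to 21 (7/28 = 25% fewer) | 5 to 4 (1/5 = 20% fewer) |
| -1 to -2 | 21 to 14 (7/21 = 33% fewer) | 4 to 3 (1/4 = 25% fewer) |
| -2 to -3 | 14 to 7 (7/14 = 50% fewer) | 3 to 3 (no change in number) |

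**The case against.** The best defence is that the Cycle 2+ text keeps the dose only if the patient is tolerating treatment in other respects. Table 7 covers grade 4 neutropenia with or without fever or infection, so a patient with a complicated episode may fail that condition, and the rules need not then clash. This stands as a limit: the first conflict is clear only for otherwise uncomplicated episodes. It does not remove the conflict, because the condition concerns matters other than the counts, and a patient whose only problem is the cytopenia meets it.

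A second defence is that Table 7 is titled as guidelines, the text after it speaks of recommendations, and the study chair can be consulted on further DEC-C changes. That softens the instructions but sets no order between them. The investigator discretion described under Table 6 is for low-grade tolerability symptoms, which grade 4 cytopenia is not. The Cycle 2+ text also points to Figures 1 and 2, whose drawings could not be read, so whether they settle the matter is unknown.

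A reader might infer more than the documents support:

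- *That the rules will clash often.* Section 1.2.2 reports grade 3/4 cytopenias in more than 50% of patients, but on DEC-C in MDS and CMML. Table 7 needs grade 4, after remission, and its reduction row needs a repeat event of 7 days or more. No frequency is given for that. The group at risk is also limited: at the planning response rates, 0.15 × 34 = 5.1 to 0.35 × 34 = 11.9 patients respond, although entry on blast clearance without CR could add some.
- *That the missing Table 7 rows are further contradictions.* A first episode over 7 days and a later one under 7 days have no row, but the Cycle 2+ rule covers both. They are gaps in the table, with one rule left to apply.

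**Conclusion.** The contradiction is real and visible in the text. For a repeat post-remission grade 4 cytopenia of 7 days or more, recovered by day 42 in a patient tolerating treatment in other respects, Table 7 lowers the dose and the Cycle 2+ text keeps it. For a first episode of 7 days or less with recovery only after 6 weeks, the instructions are reversed. Where both rules speak, they disagree in two of four combinations, and each disagreement is worth one Table 6 level.

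How many patients this touches cannot be estimated from the documents. A reader might also infer damage to the main result. That does not follow: both rules act after entry to the post-remission phase, and neither enters the Simon calculation. DLTs are defined within the pre-remission phase (Section 5.2.4), so the Table 10 boundaries are not affected either. Nor do the documents show an effect on relapse-free survival, and with a single arm there is no between-arm bias. The effect is on dosing consistency across sites, safety and exposure summaries, and the dosing correlatives.

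The conclusion assumes that Figures 1 and 2 contain no precedence rule and that 6 weeks means 42 days from day 1 of the cycle. It should be corrected, but it does not threaten the study's primary conclusion.

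**What to change.** The sponsor should reconcile the Cycle 2+ text of Section 5.2.6.3, Table 7 and the additional considerations after it into one post-remission cytopenia rule, or state which of the two triggers takes precedence. The rows of Table 7 should then be made consistent with that decision. For a first episode over 7 days and a later one under 7 days, that means adding a row or pointing to the rule that applies. No view is taken here on which rule, or which dose, is right.

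The cost is a protocol amendment to one table and one paragraph, with a sentence on precedence and the usual IRB approval at each center. Sample size, response criteria and stopping boundaries do not change.

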#### Hematologic Toxicity – Additional Considerations

If after applying the above recommendations for first and subsequent occurrences of hematologic toxicities as outlined and further dose modifications are desired for DEC-C, consider consultation with the study chair. General principles for dose modifications:

1. There will be no dose reduction of either agent based on hematologic toxicity during the pre-remission phase of this study.
2. **Within the post-remission phase, dose reductions of venetoclax and DEC-C should follow [Table 6](#).**

#### Non-hematologic Toxicity – Additional Considerations

Delay the next cycle for the following non-hematologic adverse reactions and resume at the same or reduced dose of DEC-C and venetoclax upon resolution to patient baseline or  $\leq$  Grade 1.

1. Serum creatinine  $> 2\text{mg/dl}$
2. Serum bilirubin  $> 2\text{x ULN}$
3. AST or ALT  $> 2\text{x ULN}$
4. Active or uncontrolled infection

## 5.2.8 Conditions Not Requiring Dose Reduction

The following conditions are exceptions to the dose-modification guidelines:

- Alopecia of any grade.
- Electrolyte or serum analyte (e.g., urate) abnormalities that are reversible to the patient's baseline with standard interventions.
- Isolated values of  $\geq$  Grade 3 alkaline phosphatase, defined as asymptomatic elevations in alkaline phosphatase without elevation of other liver function studies (e.g. AST/ALT or bilirubin). Determination of liver versus bone etiology should be made, and evaluation of gamma-glutamyl transferase, 5' nucleotidase, or other liver enzymes should be performed.

## 5.2.9 Venetoclax/DEC-C Dose Reduction for Decreased Glomerular Filtration Rate

- If CrCl declines during treatment and is believed to be unrelated to venetoclax/DEC-C, the dosing of these medications may be maintained provided that the patient's condition is closely monitored.
- If CrCl declines to  $< 30$  mL/min, the venetoclax should be held.

## 5.2.10 Supportive Care Recommendations for TEAEs/potential Adverse Drug Reactions occurring in conjunction with venetoclax

Supportive measures for optimal medical care include prophylaxis against tumor lysis syndrome (TLS) (see [Section 5.1.1](#))

Prophylactic anti-emetic therapy is recommended and will be prescribed at the discretion of the treating clinician.

## 5.2.11 Concomitant Medication and Treatment

Concomitant medications include any prescription or over-the-counter preparation, including vitamins, dietary supplements, and oral herbal preparations taken during the study.

Patients may continue their baseline medication(s) unless otherwise prohibited by the inclusion/exclusion criteria of study protocol and [Appendix 1](#). Any diagnostic, therapeutic, or surgical procedure performed from signing the informed consent form (CF) through 28 day follow-up should be recorded, including the dates, description of the procedure(s), and any clinical findings, if applicable.

### 5.2.11.1 Permitted Concomitant Medication

Patients will receive concomitant medications to treat symptoms, AEs, and intercurrent illnesses that are medically necessary as part of standard care. Medications to treat concomitant diseases like diabetes, hypertension, etc., are permitted.

Appropriate anti-coagulation is allowed during the study (e.g., low molecular weight heparin, direct factor Xa inhibitors, etc.). Warfarin is allowed during the study provided patients are monitored for INR twice a week during the first two cycles of therapy, then weekly to biweekly thereafter at the discretion of the treating physician.

#### **5.2.11.2 Use of Blood Products**

During treatment, patients may receive red blood cell (RBC) or platelet transfusions, if clinically indicated, per institutional guidelines. It is recommended that patients who require repeated transfusion support, in the absence of marrow disease and despite dose reductions, be discussed with the study sponsor.

#### **5.2.12 Contraception requirements**

Patients should not become pregnant or father a child while on this study because the study treatments in this study can affect an unborn baby. Women should not breastfeed a baby while on this study. It is important that patients understand the need to use birth control while on this study. Female patients of childbearing potential (See [Table 1](#), footnote 7) with male partners able to father children, defined as men without a medical/surgical cause of azoospermia, must agree to use two methods of contraception (one highly effective and one effective) and have a negative serum pregnancy test at Screening, and male patients must use an effective barrier method of contraception if sexually active with a female of childbearing potential.

**Highly effective methods include:**

- Hormonal contraceptives (e.g., combined oral contraceptives, patch, vaginal ring, injectables, and implants)
- Intrauterine device or intrauterine system
- Vasectomy or tubal ligation.

**Effective methods include:**

- Barrier methods of contraception (e.g., male condom, female condom, cervical cap, diaphragm, contraceptive sponge).

**Notes:**

No barrier method by itself achieves a highly effective standard of contraception. The proper use of diaphragm or cervical cap includes use of spermicide and is considered one barrier method.

The cervical cap and contraceptive sponge are less effective in parous women. The use of spermicide alone is not considered a suitable barrier method for contraception.

When used consistently and correctly, “double barrier” methods of contraception (e.g., male condom with diaphragm, male condom with cervical cap) can be used as an effective alternative to the highly effective contraception methods described above. Male and female condoms should not be used together as they can tear or become damaged.

Alternatively, the following fulfill the contraception requirements:

- A sexual partner who is surgically sterilized or post-menopausal as defined in See [Table 1](#), footnote 7.
- Total (true) abstinence (when this is in line with the preferred and usual lifestyle of the patient), is an acceptable method of contraception. NOTE: Periodic abstinence (e.g., calendar, ovulation, symptothermal, post-ovulation methods) and withdrawal are not acceptable methods of contraception.
- The method of acceptable contraception must be explained to both male and female potential patients. In order to be eligible for the study, patients must agree to use to use the methods of birth control described above throughout the study and for 3 months following the last dose of study treatment at the time of consent for the study. Please see [Table 1](#), footnote 7 for additional safety information related to pregnancy.

### 5.2.13 Off-Treatment Criteria

Participants will be removed from study when any of the following criteria apply:

- Disease progression
- Unacceptable toxicity
- Lost to follow-up
- Withdrawal of consent

## 5.3 Restrictions and Prohibited Medications

### Concurrent Therapies:

Concurrent therapy with any other approved or investigative anticancer therapeutic is not allowed. Other investigational agents should not be used during the study.

### Diet:

There are no dietary restrictions on this study. Patients should maintain adequate caloric and fluid intake. Grapefruit, starfruit, and Seville oranges should be avoided during the study period given interactions with CYP3A4.

### Medications:

Venetoclax should not be used with strong CYP3A inhibitors (e.g., ketoconazole, ritonavir, clarithromycin, itraconazole, voriconazole) at initiation, during ramp-up, and pre-remission phase of treatment. Concomitant use of venetoclax with moderate CYP3A inhibitors (e.g. erythromycin, ciprofloxacin, diltiazem, fluconazole, isavuconazole, verapamil), or strong CYP3A inducers (e.g. carbamazepine, phenytoin, rifampin, St. John's wort), or moderate CYP3A inducers (e.g. bosentan, efavirenz, etavirine) may be used, if clinically appropriate, during the post-remission phase with appropriate dose adjustments. See [Table 8](#) and [Appendix 1](#) for a list of representative products.

### 5.3.1 Antifungal prophylaxis

Prophylactic antifungal therapy with CYP3A4 inhibitor activity (eg, fluconazole, posaconazole, and voriconazole) are prohibited 7 days or 5 half-lives, whichever is greater, prior to C1D1 and through the pre-remission phase of therapy. Alternative antifungal therapy should be considered per institutional guidelines. During subsequent cycles, investigators may use prophylactic antifungal therapy as guided per local institutional practices. If the therapy of choice is a drug with CYP3A4 inhibitor activity, dose adjustments of venetoclax are required as detailed in [Table 8](#).

**Table 8: Drug interaction and dose reduction of venetoclax**

Drug Interaction	Dose Reduction of Venetoclax
No CYP3A or P-gp inhibitor activity	No dose reduction (400mg daily)
Posaconazole	Dose reduction to 70mg daily
Other strong CYP3A inhibitor activity (e.g., voriconazole)	Dose reduction to 100mg daily
Moderate CYP3A inhibitor activity (e.g., fluconazole; or drug with P-gp inhibitor activity)	Dose reduction at least by 50% or to 200mg daily.

### 5.4 Medication Storage

Venetoclax tablets will be obtained by the clinical team as “standard of care.” Venetoclax should be stored in accordance with written instructions provided by the patient’s pharmacy.

DEC-C will be provided by the study sponsor in high-density polyethylene (HDPE) bottle with a child resistant closure. Each bottle contains either 1 or 2 desiccant canisters for moisture absorption. The desiccant canisters should remain in the bottle at all times and must not be ingested. DEC-C is store at controlled room temperature (20 – 25°C) in the original package provided.

### 5.5 Study Drug Accountability

Venetoclax will be obtained standard of care by the patient’s treatment team.

DEC-C will be provided by the study sponsor. Sites must request study drug by submitting an order form directly to the drug supplier for the study drug to be shipped to

the site pharmacy. The investigator or designee will verify and acknowledge receipt of all study drug shipments by signing and returning all required forms.

Overall study drug accountability and destruction records (DEC-C only) will be maintained by the Sponsor-Investigator. The investigator, or a responsible party designated by the investigator, must maintain a careful record of the inventory and disposition of unused material.

DEC-C should not be used for any purpose outside the scope of this protocol, nor may it be transferred or licensed to any party not participating in the clinical study. Data for DEC-C is confidential/proprietary and shall be maintained as such by the investigators.

All drug supplies provided by the drug supplier must be kept in an appropriate, limited access, secure place until used or returned to the drug supplier for destruction. Drug supplies will be counted and reconciled at the site before being returned.

